2.9 Rationale for targeting patients with triple negative breast cancer

Triple-negative breast cancer (TNBC) lacks expression of estrogen receptor, progesterone receptor and HER-2. TNBC is associated with an aggressive clinical course, and there are no targeted therapies available. As such, development of innovative therapies for the treatment of TNBC is an important priority.

There is strong rationale for the use of checkpoint blockade therapy in patients with TNBC.

First, TNBC is a mutationally complex breast cancer subtype. Previous studies suggest that response to checkpoint blockade therapy is associated with mutational load. Several recent studies have provided insight into the mutational landscape in human breast cancer, including TNBC. While the average somatic mutational frequency across almost 30 different types of cancer is approximately one mutation/megabase, the frequency among all breast cancers ranges from 0.1 to 10 [54-56]. One feature of TNBC is the increased frequency of germline and somatic TP53 and BRCA1 mutations [57]. TP53 and BRCA mutations lead to defects in DNA repair mechanisms, and consequently an increased mutational frequency. Extensive analysis of the clonal and mutational spectrum of primary TNBC suggests that TNBC is characterized by a higher mutational frequency than other subtypes of breast cancer [58, 59]. The relative abundance of somatic mutations in TNBC compared to other breast cancer subtypes suggests that mutant antigens that can be targeted by the immune system are more likely to be present.

Second, tumor infiltrating lymphocytes (TILs) are more common in TNBC, and TILs are associated with improved outcome in TNBC following adjuvant or neoadjuvant chemotherapy [60-62]. The association between TILs and improved outcome in TNBC suggests that the adaptive immune system contributes to the response to chemotherapy.

Third, PD-L1 expression is higher in TNBC than other breast cancer subtypes [63, 64]. PD-L1 expression has been used as a biomarker for response to checkpoint blockade therapy [65].

We have examined the expression of PD-1 and PD-L1 in the common molecular subtypes of breast cancer using a well annotated human breast cancer tissue array [64, 66]. These studies demonstrate that expression of PD-1 on tumor-infiltrating lymphocytes and/or PD-L1 on breast cancers is more common in TNBC, and expression of these proteins is associated with a poor prognosis. Other investigators have also documented increased expression of PD-L1 in TNBC [63].

Fourth, a recent phase 1 clinical trial of atezolizumab in patients with metastatic TNBC demonstrates the safety of checkpoint blockade therapy with promising response rates. In an oral presentation at the AACR annual meeting in April 2015 (Abstract 2859), Emens et al. reported on 54 patients with metastatic TNBC enrolled in an expansion cohort. Patients received atezolizumab at 15 mg/kg, 20 mg/kg or 1200 mg flat dose IV q3w. AEs occurred in 67% of patients, most frequently fatigue (22%), pyrexia (15%), neutropenia (15%), and nausea (15%). Grade 3 AEs occurred in 11% of patients (adrenal insufficiency, neutropenia, nausea, vomiting, decreased WBC count). Twenty-one of the 54 patients were evaluable for efficacy, all of whom were PD-L1-positive (IHC 2/3). Among the 21 evaluable patients with PD-L1-expressing tumors, the unconfirmed RECIST ORR was 24% (95% CI, 8% to 47%) which included 3 PRs and 2 CRs.

Adams et al reported the results of a phase 1b clinical trial of atezolizumab in combination with nab-paclitaxel in patients with metastatic TNBC at the 2015 SABCs Meeting (Abstract P2-11-06). Twenty-four

patients with a minimum follow-up of ≥ 3 months were evaluable for efficacy. Across all groups the ORR was 71%. Based on these tests, a randomized phase 3 trial is planned (Impassion130, NCT02425891).

2.10 Durvalumab (MEDI4736)

The non-clinical and clinical experience is fully described in the most current version of the durvalumab Investigator's Brochure (edition 10).

Durvalumab is a human monoclonal antibody (mAb) of the immunoglobulin G (IgG) 1 kappa subclass that inhibits binding of PD-L1 and is being developed by AstraZeneca/MedImmune for use in the treatment of cancer. (MedImmune is a wholly owned subsidiary of AstraZeneca; AstraZeneca/MedImmune will be referred to as AstraZeneca throughout this document.) As durvalumab is an engineered mAb, it does not induce antibody-dependent cellular cytotoxicity or complement-dependent cytotoxicity. The proposed mechanism of action for durvalumab is interference of the interaction of PD-L1 with PD-1 and CD80. PD-L1 can bind to both PD-1 and CD80 on T cells. Similar to PD-L1/PD-1, the PD-L1/CD80 interaction delivers an inhibitory signal in T cells. Blockade of the PD-L1/CD80 interaction is expected to block the inhibitory signal and thereby enhance T cell responsiveness and expansion.

To date durvalumab has been given to more than 1800 subjects as part of ongoing studies either as monotherapy or in combination with other anti-cancer agents. Details on the safety profile of durvalumab monotherapy are summarized in Section 2.10.1. Refer to the current durvalumab Investigator's Brochure for a complete summary of non-clinical and clinical information including safety, efficacy and pharmacokinetics.

2.10.1 Durvalumab monotherapy dose rationale

A durvalumab dose of 20 mg/kg Q4W is supported by in-vitro data, non-clinical activity, clinical PK/pharmacodynamics, biomarkers, and activity data from Study 1108 in subjects with advanced solid tumors and from a Phase I trial performed in Japanese subjects with advanced solid tumor (D4190C00002).

2.10.2 PK/Pharmacodynamic data

Based on available PK/pharmacodynamic data from ongoing Study 1108 with doses ranging from 0.1 to 10 mg/kg Q2W or 15 mg/kg Q3W, durvalumab exhibited non-linear (dose-dependent) PK consistent with target-mediated drug disposition. The PK approached linearity at ≥ 3 mg/kg Q2W, suggesting near complete target saturation (membrane-bound and sPD-L1), and further shows that the durvalumab dosing frequency can be adapted to a particular regimen given the linearity seen at doses higher than 3 mg/kg. The expected half-life with doses ≥ 3 mg/kg Q2W is approximately 21 days. A dose-dependent suppression in peripheral sPD-L1 was observed over the dose range studied, consistent with engagement of durvalumab with PD-L1. A low level of immunogenicity has been observed. No subjects have experienced immune-complex disease following exposure to durvalumab (For further information on immunogenicity, please see the current IB).

Data from Study D4190C00006 (Phase I trial in NSCLC subjects using the combination of durvalumab and tremelimumab) also show an approximately dose-proportional increase in PK exposure for durvalumab over the dose range of 3 to 20 mg/kg durvalumab Q4W or Q2W. (For further information on PK observations in Study 006, please see the current IB).

The observed durvalumab PK data from the combination study were well in line with the predicted monotherapy PK data (5th median and 95th percentiles) for a Q4W regimen.

A population PK model was developed using the data from Study 1108 (doses=0.1 to 10 mg/kg Q2W or 15 mg/kg Q3W (Fairman et al 2014)). Multiple simulations indicate that a similar overall exposure is expected following both 10 mg/kg Q2W and 20 mg/kg Q4W regimens, as represented by AUC_{ss} (4 weeks). Median C_{max,ss} is expected to be higher with 20 mg/kg Q4W (~1.5 fold) and median C_{trough,ss} is expected to be higher with 10 mg/kg Q2W (~1.25 fold). Clinical activity with the 20 mg/kg Q4W dosing regimen is anticipated to be consistent with 10 mg/kg Q2W with the proposed similar dose of 20 mg/kg Q4W expected to (a) achieve complete target saturation in majority of subjects; (b) account for anticipated variability in PK, pharmacodynamics, and clinical activity in diverse cancer populations;

(c) maintain sufficient PK exposure in case of ADA impact; and (d) achieve PK exposure that yielded maximal antitumor activity in animal models.

Given the similar area under the plasma drug concentration-time curve (AUC) and modest differences in median peak and trough levels at steady state, the observation that both regimens maintain complete sPD-L1 suppression at trough, and the available clinical data, the 20 mg/kg Q4W and 10 mg/kg Q2W regimens are expected to have similar efficacy and safety profiles, supporting further development with a dose of 20 mg/kg Q4W.

2.10.3 Clinical data

Refer to the current durvalumab Investigator's Brochure for a complete summary of clinical information including safety, efficacy and pharmacokinetics at the 20mg/kg Q4W regimen.

2.10.4 Rationale for fixed dosing

A population PK model was developed for durvalumab using monotherapy data from a Phase I study (study 1108; N=292; doses= 0.1 to 10 mg/kg Q2W or 15 mg/kg Q3W; solid tumors). Population PK analysis indicated only minor impact of body weight (WT) on the PK of durvalumab (coefficient of ≤ 0.5). The impact of body WT-based (10 mg/kg Q2W) and fixed dosing (750 mg Q2W) of durvalumab was evaluated by comparing predicted steady state PK concentrations (5th, median and 95th percentiles) using the population PK model. A fixed dose of 750 mg was selected to approximate 10 mg/kg (based on median body WT of ~75 kg). A total of 1000 subjects were simulated using body WT distribution of 40–120 kg. Simulation results demonstrate that body WT-based and fixed dosing regimens yield similar median steady state PK concentrations with slightly less overall between-subject variability with fixed dosing regimen.

Similar findings have been reported by others (Ng et al 2006, Wang et al 2009, Zhang et al 2012, Narwal et al 2013). Wang and colleagues investigated 12 monoclonal antibodies and found that fixed and body size-based dosing perform similarly, with fixed dosing being better for 7 of 12 antibodies (Wang et al 2009)]. In addition, they investigated 18 therapeutic proteins and peptides and showed that fixed dosing performed better for 12 of 18 in terms of reducing the between-subject variability in pharmacokinetic/pharmacodynamics parameters (Zhang et al 2012).

A fixed dosing approach is preferred by the prescribing community due to ease of use and reduced dosing errors. Given expectation of similar pharmacokinetic exposure and variability, we considered it feasible to switch to fixed dosing regimens. Based on average body WT of 75 kg, a fixed dose of 1500 mg Q4W durvalumab (equivalent to 20 mg/kg Q4W) is included in the current study.

2.10.5 Identified and potential risks

Monoclonal antibodies directed against immune checkpoint proteins, such as programmed cell death ligand 1 (PD-L1) as well as those directed against programmed cell death-1 (PD-1) or cytotoxic T-lymphocyte antigen-4 (CTLA-4), aim to boost endogenous immune responses directed against tumor cells. By stimulating the immune system however, there is the potential for adverse effects on other tissues.

Most adverse drug reactions seen with the immune checkpoint inhibitor class of agents are thought to be due to the effects of inflammatory cells on specific tissues. Potential risks are events with a potential inflammatory mechanism and which may require more frequent monitoring and/or unique interventions such as immunosuppressants and/or endocrine replacement therapy. These risks include gastrointestinal AEs such as colitis and diarrhoea, pneumonitis, nephritis and acute renal failure, hepatic AEs such as hepatitis and liver enzyme elevations, dermatitis, and endocrinopathies such as hypo- and hyper-thyroidism, hypophysitis and adrenal insufficiency.

Identified risks with durvalumab are diarrhea, increases in transaminases, pneumonitis and colitis.

Potential risks include endocrinopathies (hypo- and hyper-thyroidism, hypophysitis and adrenal insufficiency) hepatitis/hepatotoxicity, neurotoxicities, nephritis, pancreatitis, dermatitis, infusion-related reactions, anaphylaxis, hypersensitivity or allergic reactions, and immune complex disease. Further information on these risks can be found in the current version of the durvalumab IB.

In monotherapy clinical studies AEs (all grades) reported very commonly ($\geq 10\%$ of subjects) are fatigue, nausea, decreased appetite, dyspnea, cough, constipation, diarrhea, vomiting, back pain, pyrexia, abdominal pain, anemia, arthralgia, peripheral edema, headache, rash, and pruritus. Approximately 10% of subjects experienced an AE that resulted in permanent discontinuation of durvalumab and approximately 3.5% of subjects experienced an SAE that was considered to be related to durvalumab by the study investigator.

The majority of treatment-related AEs were manageable with dose delays, symptomatic treatment, and in the case of events suspected to have an immune basis, the use of established treatment guidelines for immune-mediated.

A detailed summary of durvalumab monotherapy AE data can be found in the current version of the durvalumab IB

3 PATIENT SELECTION

3.1 Eligibility Criteria

3.1.1 Inclusion criteria

A patient will be eligible for inclusion in this study only if ALL of the following criteria apply:

- (1) Histologically confirmed diagnosis of invasive breast cancer.
- (2) ER and PR less than Allred score of 3 or less than 1% positive staining cells in the invasive component of the tumor. Patients not meeting this pathology criteria, but have been clinically treated as having TNBC, may be enrolled at treating physician's discretion.
- (3) HER2 negative by FISH or IHC staining 0 or 1+.
- (4) Consented for genome sequencing.
- (5) Clinical stage T1c-T4c, any N, M0 primary tumor by AJCC 7th edition clinical staging prior to neoadjuvant chemotherapy, with residual invasive breast cancer after neoadjuvant therapy.
- (6) At least 18 years of age.
- (7) Eastern Cooperative Oncology Group (ECOG) performance status ≤ 1 .
- (8) Adequate organ and marrow function no more than 14 days prior to registration as defined below:

absolute neutrophil count	$\geq 1,500/\mu\text{L}$
platelets	$\geq 100,000/\mu\text{L}$
hemoglobin	$\geq 9.0 \text{ g/dL}$
total bilirubin	$\leq 1.5 \text{ X institutional upper limit of normal}$
AST/ALT	$\leq 2.5 \text{ X institutional upper limit of normal}$
serum creatinine clearance	$> 40 \text{ mL/min}$ by the Cockcroft-Gault formula or by 24-hour urine collection for determination of creatinine clearance
- (9) Body weight $> 30 \text{ kg}$.
- (10) Evidence of post-menopausal status or negative urine or serum pregnancy test for female pre-menopausal subjects. Women will be considered post-menopausal if they have been amenorrheic for 12 months without an alternative medical cause. The following age-specific requirements apply:
 - Women < 50 years of age would be considered post-menopausal if they have been amenorrheic for 12 months or more following cessation of exogenous hormonal treatments and if they have luteinizing hormone and follicle-stimulating hormone levels in the post-menopausal range for the institution or underwent surgical sterilization (bilateral oophorectomy or hysterectomy).
 - Women ≥ 50 years of age would be considered post-menopausal if they have been amenorrheic for 12 months or more following cessation of all exogenous hormonal treatments, had radiation-induced menopause with last menses > 1 year ago, had chemotherapy-induced menopause with last menses > 1 year ago, or underwent surgical sterilization (bilateral oophorectomy, bilateral salpingectomy, or hysterectomy).
- (11) Able to understand and willing to sign an IRB-approved written informed consent document.

3.1.2 Exclusion criteria

A patient will be ineligible for inclusion in this study if ANY of the following criteria apply:

- (1) Received chemotherapy, radiotherapy (to more than 30% of the bone marrow or with a wide field of radiation), or biologic therapy within the last 30 days.
- (2) Concurrent enrollment in another clinical study, unless it is an observational (non-interventional) clinical study or during the follow-up period of an interventional study.

- (3) Receiving any other investigational agent(s) or has received an investigational agent within the last 30 days.
- (4) Receipt of live attenuated vaccination within 6 months prior to study entry or within 30 days of receiving durvalumab.
- (5) Major surgical procedure within 28 days prior to the first dose of durvalumab. Local surgery of isolated lesions for palliative intent is acceptable.
- (6) Current use or prior use of immunosuppressive medication within 28 days before the first dose of durvalumab, with the exceptions of intranasal, inhaled, and intra-articular corticosteroids or systemic corticosteroids at physiological doses which are not to exceed 10 mg/day of prednisone or an equivalent corticosteroid.
- (7) Known metastatic disease.
- (8) Invasive cancer in the contralateral breast.
- (9) Known allergy, or history of serious adverse reaction to vaccines such as anaphylaxis, hives, or respiratory difficulty.
- (10) History of hypersensitivity to durvalumab or any excipient.
- (11) Mean QT interval corrected for heart rate using Fridericia's formula (QTcF) \geq 470 ms calculated from 3 electrocardiograms (ECGs) (within 15 minutes at 5 minutes apart).
- (12) Any unresolved toxicity NCI CTCAE grade \geq 2 from previous anticancer therapy with the exception of alopecia, vitiligo, and the laboratory values defined in the inclusion criteria. Subjects with grade \geq 2 neuropathy will be evaluated on a case-by-case basis after consultation with the study physician. Subjects with irreversible toxicity not reasonably expected to be exacerbated by treatment with durvalumab may be included only after consultation with the study physician.
- (13) Uncontrolled intercurrent illness including, but not limited to ongoing or active infection, symptomatic congestive heart failure, uncontrolled hypertension, unstable angina pectoris, cardiac arrhythmia, interstitial lung disease, serious chronic gastrointestinal conditions associated with diarrhea, evidence of any acute or chronic viral illness or disease, or psychiatric illness/social situation that would limit compliance with study requirements or compromise the ability of the subject to give written informed consent.
- (14) Active or prior documented autoimmune or inflammatory disorders (including inflammatory bowel disease [e.g., colitis or Crohn's disease], diverticulitis [with the exception of diverticulosis], systemic lupus erythematosus, Sarcoidosis syndrome, or Wegener syndrome [granulomatosis with polyangiitis, Graves' disease, rheumatoid arthritis, hypophysitis, uveitis, etc.]). The following are exceptions to this criterion:
 - Subjects with vitiligo or alopecia
 - Subjects with hypothyroidism (e.g., following Hashimoto syndrome) stable on hormone replacement
 - Any chronic skin condition that does not require systemic therapy
 - Subjects without active disease in the last 5 years may be included but only after consultation with the study physician
 - Subjects with celiac disease controlled by diet alone
- (15) History of pneumonitis or interstitial lung disease.
- (16) History of active primary immunodeficiency.
- (17) Active infection including tuberculosis (clinical evaluation that includes clinical history, physical examination, and radiographic findings, and TB testing in line with local practice), hepatitis B (known positive HBV surface antigen (HBsAg) result), hepatitis C, or human immunodeficiency virus (positive HIV 1/2 antibodies). Subjects with a past or resolved HBV infection (defined as the presence of

hepatitis B core antibody (anti-HBc) and absence of HBsAg) are eligible. Subjects positive for hepatitis C (HCV) antibody are eligible only if polymerase chain reaction is negative for HCV RNA.

- (18) History of allogeneic organ transplantation.
- (19) Pregnant or breastfeeding. A negative serum pregnancy test is required no more than 14 days before study entry.
- (20) Subjects of reproductive potential who are not willing to employ effective birth control from screening to 1 year after last dose of vaccine.
- (21) History of another primary malignancy except for:
- Malignancy treated with curative intent and with no known active disease \geq 5 years before the first dose of study treatment and low potential for risk of recurrence
 - Adequately treated non-melanoma skin cancer of lentigo maligna without evidence of disease
 - Adequately treated carcinoma in situ without evidence of disease
- (22) History of leptomeningeal carcinomatosis.
- (23) Patient must have no active major medical or psychosocial problems that could be complicated by study participation.
- (24) Subjects with a strong likelihood of non-adherence such as difficulties in adhering to follow-up schedule due to geographic distance from the Siteman Cancer Center should not knowingly be registered.
- (25) Individuals in whom a skinfold measurement of the cutaneous and subcutaneous tissue for eligible injection sites (left and right medial deltoid region) exceeds 40 mm.
- (26) Individuals in whom the ability to observe possible local reactions at the eligible injection sites (deltoid region) is, in the opinion of the investigator, unacceptably obscured due to a physical condition or permanent body art.
- (27) Therapeutic or traumatic metal implant in the skin or muscle of either deltoid region.
- (28) Acute or chronic, clinically significant hematologic, pulmonary, cardiovascular, or hepatic or renal functional abnormality as determined by the investigator based on medical history, physical examination, EKG, and/or laboratory screening test
- (29) Any chronic or active neurologic disorder, including seizures and epilepsy, excluding a single febrile seizure as a child, or chronic seizure disorder which is well controlled by medication with no seizures within the last 2 years.
- (30) Syncopal episode within 12 months of screening
- (31) Current use of any electronic stimulation device, such as cardiac demand pacemakers, automatic implantable cardiac defibrillator, nerve stimulators, or deep brain stimulators.

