- Study Design:** This is a single institution, open-label randomized phase 1 trial of neoantigen DNA vaccine alone vs. neoantigen DNA vaccine plus durvalumab in triple negative breast cancer (TNBC) patients who have residual disease following standard of care therapy. Patients with newly diagnosed clinical stage II-III TNBC are eligible for enrollment. Patients will receive standard of care therapy including chemotherapy, surgery and radiation therapy as clinically indicated. Following standard of care therapy, patients will be randomized to receive either a neoantigen DNA vaccine alone, or a neoantigen DNA vaccine + durvalumab.
- Hypotheses:** Hypotheses tested in this study include: (1) neoantigen DNA vaccines can induce and/or enhance neoantigen-specific T cell responses; and (2) durvalumab will enhance the response to neoantigen DNA vaccines.
- Objectives:** The primary objective is to assess the safety of neoantigen DNA vaccines given alone or in combination with durvalumab. Safety assessment will include both clinical observation and laboratory evaluation. The secondary objective is to measure the immune response to neoantigen DNA vaccines given alone, or in combination with durvalumab. The immune response will be measured in the peripheral blood by luminex assay, ELISPOT, and multiparametric flow cytometry.
- Product Description:** The neoantigen DNA vaccines are composed of closed circular DNA plasmids that are designed to express neoantigens identified by next generation sequencing. The plasmids will be formulated as naked DNA plasmid vaccines, and supplied at a concentration of 2 mg/mL. DNA vaccines will be administered intramuscularly (in the deltoid or lateralis) using a TriGrid electroporation device (Ichor Medical Systems). Two injections (2 mg/injection, total dose 4 mg) will be administered at each time point.
- Durvalumab is a human monoclonal antibody (MAb) of the immunoglobulin G1 kappa (IgG1 κ) subclass that inhibits binding of programmed cell death ligand 1 (PD-L1) to programmed cell death 1 (PD-1) and CD80 (B7-1).
- Subjects:** Patients with clinical stage II-III TNBC are eligible for participation. Patients must provide consent for tumor/normal exome sequencing and dbGAP-based data sharing and provide germline and tumor DNA samples of adequate quality for exome and cDNA-capture sequencing.

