6.4 Product formulation

The eluted plasmid preparations will be resuspended in sterile, preservative free-PBS. A small sample (100 µL) will be removed aseptically and the concentration tested using a certified NanoDrop spectrophotometer, Qubit Fluorometer or similar device. Typically, the eluted DNA is in the range of 3-4 mg/mL. The DNA product will be diluted to 2 mg/mL using sterile, preservative-free PBS, and aseptically added to 2.0 mL cryovials from Nalgene (Catalog# 5000-0020, Lot# 616412). The vials are made of polypropylene with a high-density polyethylene closure. They are externally-threaded for aseptic technique. They have a sealing ring in conjunction with specially designed threads. A white marking area, fill line, and graduations are printed on the vials with white paint. They are radiation-sterilized, non-cytotoxic, non-pyrogenic, and are RNase/DNase-free.

We plan to synthesize enough DNA for approximately 20 vials. We anticipate that 12 vials will be required for vaccination (2 vials per time point times 6 time points), and 5 vials will be required for product release tests. We are targeting 20 vials to have a reserve stock.

Following vialing, we anticipate that 4 vials (#1, 4, 10, 19) will be used for product release testing. Vials 1 and 19 will be used to test sterility and represent the beginning and end of the vialing procedure. Two additional vials will be used for the other product release tests listed in Table 3.

If any contamination would be detected in our plasmid samples, we would initiate an alcohol precipitation step. This procedure is basically the final stage of the gigaprep purification, where the soluble DNA is

precipitated using 2x volumes of cold isopropanol and the DNA is pelleted by centrifugation. The pellet is washed in 70% ethanol and air dried. This procedure is a standard method for eliminating any microbiologic contamination in DNA.

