8 TREATMENT PLAN

8.1 Neoantigen DNA vaccine administration

The first neoantigen DNA vaccine injection will take place following completion of SOC therapy. The day of the first vaccine injection will be referred to as Day 1.

All subjects will be treated as outpatients in the Siteman Cancer Center.

The schedule of vaccination is Day 1, Day 29 \pm 7, Day 57 \pm 7, Day 85 \pm 7, Day 113 \pm 7, and Day 141 \pm 7 with at least 21 days between injection days. All study injections will be given intramuscularly using an integrated electroporation device (TDS-IM system, Ichor Medical Systems). At each vaccination time point, patients will receive two injections of the neoantigen DNA vaccine, one injection into each deltoid or lateralis. If both injections cannot be given on the same day, the patient will be asked to return to complete the second injection. Standard aseptic technique and precautions will be utilized in site preparation, vaccine administration, and medical waste disposal to ensure maximal safety of subjects and study personnel. Participants' vital signs will be monitored for 30 minutes post vaccine for safety purposes.

The propagation of electroporation inducing electrical fields in the muscle will result in brief, localized muscle contractions at the site of administration, which are transiently painful. The neoantigen DNA vaccines will be administered by an experienced nurse who has completed a training seminar on the use of the TDS-IM device.

The sites of immunization may be rotated for each of the immunizations. No injection will be given at a location in which the draining lymph nodes have been removed.

At the discretion of the treating physician, patients may be pre-medicated with lorazepam 1mg PO (or similar) at least 30 minutes but no greater than 60 minutes prior to the first injection. Patients may also receive a second dose of lorazepam (1 mg PO) (or similar) 10 minutes prior to injection. Patients may also receive pain medication at treating physicians' discretion PO at least 30 minutes but no greater than 60 minutes prior to the first injection.

At intervals throughout the study (both before and after vaccination) subjects will have blood drawn for immunologic assays. Any cells, serum or plasma not used will be stored for future immunological assays.

Please see **Section 10 Study Calendar** for details on study visit procedures and monitoring.

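### The metal-implant and visibility exclusions check only the deltoids, although 8.1 also allows the lateralis and makes its use foreseeable when one deltoid is barred

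*Combined protocol and SAP*

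**What the plan says.** Three exclusions in 3.1.2 depend on the injection site, and all three name the deltoid alone:

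- (25) sets a skinfold limit and identifies the sites: "eligible injection sites (left and right medial deltoid region) exceeds 40 mm".
- (26) concerns "the ability to observe possible local reactions at the eligible injection sites (deltoid region"), judged by the investigator.
- (27) excludes a patient for "Therapeutic or traumatic metal implant in the skin or muscle of either deltoid region".

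The administration text is wider. The Product Description in the synopsis states: "DNA vaccines will be administered intramuscularly (in the deltoid or lateralis) using a TriGrid electroporation device". Section 8.1 calls for "one injection into each deltoid or lateralis" at each vaccination. It lets sites change between vaccinations and forbids injection where the draining lymph nodes are gone. Section 6.9 requires the two injections at a time point to be at separate sites.

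On dose, the synopsis states: "Two injections (2 mg/injection, total dose 4 mg) will be administered at each time point". Section 6.4 counts supplies on the same basis: "12 vials will be required for vaccination (2 vials per time point times 6 time points").

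**The concern.** The criteria and the administration section disagree about where vaccine may go. (25) and (26) treat the deltoids as the eligible sites; the synopsis and 8.1 add a second muscle. The safety checks follow the narrower list.

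The lateralis is not a remote option. Patients may have any nodal stage and must have residual invasive cancer after neoadjuvant therapy (inclusion 5), and the synopsis expects surgery as part of standard care. Where axillary nodes on one side have been removed, the 8.1 rule takes that deltoid away. Because two separate sites are needed each time, the only other site that 8.1 names is the lateralis.

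For such a patient the check falls on the wrong muscle. Metal in the barred deltoid, which will never be injected, excludes her. Metal in the lateralis that will be electroporated does not. Local signs and symptoms are the first parameter listed for the primary safety objective in 11.1, so a site where reactions cannot be seen also bears on what the trial sets out to measure. Metal is the main matter and visibility the lesser one.

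**Working it through.** **Inputs**

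- Injections per time point: 2 (synopsis; 8.1)
- Time points: 6, on Days 1, 29, 57, 85, 113 and 141 (8.1)
- DNA per injection: 2 mg (synopsis)

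**The plan's own figure.** Injections per patient = 2 × 6 = 12. This equals the 12 vials in 6.4. Planned dose = 12 × 2 mg = 24 mg.

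**Injections into the lateralis.** If every available deltoid is used at each visit, the lateralis count is 6 × (number of deltoids barred). Nothing in 8.1 caps lateralis use, so the permitted maximum is 12 in every row.

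| Deltoids barred | Lateralis injections if open deltoids are always used | Permitted maximum |
|---|---|---|
| 0 | 6 × 0 = 0 | 12 |
| 1 | 6 × 1 = 6 | 12 |
| 2 | 6 × 2 = 12 | 12 |

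With one deltoid barred, the lateralis receives 6 × 2 mg = 12 mg, and 12 / 24 = 0.5 of the planned dose. Losing both deltoids to node removal is less likely, because exclusion (8) rules out invasive cancer in the other breast.

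**Does another provision cover the lateralis?**

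- (28) concerns blood, lung, heart, liver and kidney abnormalities, not injection sites.
- (31) begins "Current use of any electronic stimulation device" and covers powered devices such as pacemakers, not passive metal.
- (23) covers active major medical or psychosocial problems; a healed implant does not obviously qualify.
- 6.9.6 describes an automated check before injection, and 9.1.3 describes circuits that limit energy. Neither is said to detect metal.
- The study calendar schedules a physical exam at screening, at the eligibility re-check and at each vaccination visit, but ties none of them to an injection site.

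No visible criterion therefore supplies a metal or visibility check at the lateralis. Adding one, or removing the lateralis option, brings the number of injections into an unchecked site to 0.

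**The case against.** The strongest reply is that the exposure is narrow and perhaps handled elsewhere. Everyone enrolled has passed the site checks at both deltoids. Harm would need a patient who has metal in the skin or muscle of the lateralis, or obscured skin there, and who is also injected there. The documents give no frequency for that. The device risks in 9.1.3 do not mention metal, so the hazard is inferred from the existence of (27). Section 6.9.2 refers to a user manual and study-specific procedures, 6.9.6 to a user's guide, and 9.1.3 to precautions explained in the consent form; any of these may contain a site rule. A trained nurse gives each injection.

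Most of this stands and keeps the point small. It does not remove it. The plan itself treats metal at a deltoid as reason to exclude, and gives no reason why the same finding should be acceptable at the other permitted site. Documents that cannot be seen can neither confirm nor rule out a check, so the point is confined to the eligibility criteria and 8.1.

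A reader might infer that the plan sends all 12 injections to an unchecked muscle. The documents do not support that: it would mean passing over two checked deltoids or losing both. A reader might also count the 40 mm skinfold limit in (25) as part of the fault. The documents give no reason for that limit and no lateralis value, so no harm can be shown from its absence there.

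**Conclusion.** The inconsistency is real and minor. In a patient with one deltoid barred and the other always used, 6 of 12 injections (12 of 24 mg) would foreseeably go into a lateralis that no visible eligibility criterion has checked for metal or visibility.

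This rests on three assumptions: that removing axillary nodes bars the deltoid on that side under 8.1; that the second injection then goes to the lateralis, the only other site named; and that no unseen document supplies the check. The number of patients affected is not stated and cannot be estimated from the documents.

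It would go too far to conclude that the trial has no safeguard against metal at the lateralis, since the device manual or study procedures may hold one. Sample size, power and alpha are unaffected.

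**What to change.** Keep (26) and (27) as they stand for the deltoids. Limiting them to the sites intended for each patient would relax the present rule, because a patient with deltoid metal could then enrol for lateralis injection.

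Add to 8.1 that no injection is given in a lateralis with a metal implant in the skin or muscle, or where local reactions cannot be observed. Confirm this at the physical exam already scheduled at the eligibility re-check, which comes before randomization (4.6 and the study calendar). Placed in 8.1, the rule bars the site and not the patient, which an exclusion criterion could not do.

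Alternatively, delete the lateralis from the synopsis and 8.1, and state where the second injection goes when one deltoid is barred.

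Two changes should not be made on present information. Leave (25) alone unless the device's specifications give a lateralis value. Do not fall back on two injections in one muscle unless the device supplier confirms it: 6.9.4 reports up to 4.0 mg in one muscle as a single injection, and paired injections only in two separate muscle sites.

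The cost is a short amendment, a brief look at an exam already planned, and a few patients restricted to other sites.
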